#### 9.4.9 COST-EFFECTIVENESS ANALYSIS

We will analyze the cost-effectiveness of the dDPP and hDPP for a 12-month and lifetime horizon. For the 12-month horizon, we will evaluate the differences in costs and effects for participants in the dDPP and hDPP study arms. We do not anticipate substantial differences in healthcare utilization during the 12 months of the trial between the two arms, as participants have prediabetes rather than overt diabetes, and most relevant healthcare expenditures are expected to occur at the diabetes stage. For the lifetime horizon, we will construct a Markov model with model parameters populated from the trial results as well as other published literature. For example, we will estimate the cost savings associated with intermediate endpoints, such as percentage weight loss reduction, A1C reduction, or increased physical activity levels. Both analyses will be conducted from a health system perspective. Future costs and effects will be discounted at 3%.

##### **Markov Model**

For the lifetime horizon analysis, we will construct a Markov model to simulate hypothetical patients exposed to either a dDPP or hDPP. The model will consist of health states reflective of prediabetes and diabetes such as normal glucose tolerance, impaired fasting glucose, impaired glucose tolerance, type 2 diabetes mellitus, and death. The transition probabilities between these health states will be calculated using data from the trial and published literature as needed. Again, given the relatively short duration of this trial, we do not expect a significant number of participants to convert from prediabetes to overt diabetes. Rather, we will estimate future diabetes incidence based on change in A1C as a proxy based on previously published studies. Life table estimates from the Centers for Disease Control and Prevention will be used to determine probabilities of death in all health states.

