### 2.2 BACKGROUND

Prediabetes affects more than one-third of US adults. It is projected that more than 470 million people worldwide will carry a diagnosis of prediabetes by 2030. Considering that the microvascular and macrovascular complications associated with type 2 diabetes begin at the prediabetes stage and that more than half of individuals with prediabetes will eventually develop diabetes, **efforts are urgently needed to intervene early on this large high-risk population.** Prediabetes has been linked to an approximately 20% increased risk of cardiovascular disease, with cross-sectional data from the National Health and Nutrition Examination Survey (NHANES) showing surprisingly similar rates of myocardial infarction and stroke among people with prediabetes and overt diabetes. Prediabetes has also been linked to a 15% increased risk of developing cancer and a 14% higher cancer mortality rate. Studies have also found negative neurological sequelae in prediabetic patients, including slower processing speed, dementia, stroke, and depression.

A recent systematic review and meta-analysis of 53 U.S. based studies found that **lifestyle programs modeled on the DPP are effective** across diverse settings and populations. Real-world diet and exercise programs have been shown to reduce the incidence of diabetes by 41% and body weight by 2.2%. These translational DPPs are recognized by the CDC, which maintains a national registry of DPPs; however, there are only 1,530 recognized programs in the US, or 1 program per ~55,000 affected US adults with prediabetes, which makes it highly unlikely that all patients who need these services can access them. The **rural/urban DPP access divide** is large, with 14.6% and 48.4% of rural and urban counties, respectively, having access to a national DPP site.

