##### **Effects**

The effects for the cost-effectiveness analysis will be Quality-adjusted life years (QALYs). QALYs were selected because of their ability to capture both morbidity and mortality domains of health and they are used across existing literature. The calculation of QALYs will be based on a patient's time spent in a specific health state multiplied by the utility weight for that respective of the state. Utility weights will be derived from published literature. For the 12-month analysis horizon, the time spent in each health state will be estimated using trial data. For the lifetime analysis horizon, a utility weight will be assigned to each health state and the running of the Markov model will provide the time spent for a hypothetical patient in each health state over their lifetime.

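### The lifetime model takes deaths in every state from one life table and states no mortality ratio for diabetes, so, as written, preventing diabetes adds no life-years and the QALY difference is attenuated

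*Combined protocol and SAP*

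**What the plan says.** Section 9.4.9 plans a 12-month and a lifetime cost-effectiveness analysis. The lifetime one is a Markov model whose states are introduced as examples: "normal glucose tolerance, impaired fasting glucose, impaired glucose tolerance, type 2 diabetes mellitus, and death". On movement between states the Markov Model paragraph says: "The transition probabilities between these health states will be calculated using data from the trial and published literature as needed". Few conversions to diabetes are expected during the trial, so the effect is carried forward indirectly: "we will estimate future diabetes incidence based on change in A1C as a proxy based on previously published studies". On mortality there is one sentence: "Life table estimates from the Centers for Disease Control and Prevention will be used to determine probabilities of death in all health states".

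Under Effects, the outcome is the QALY, with this reason: "QALYs were selected because of their ability to capture both morbidity and mortality domains of health". For the lifetime horizon, "a utility weight will be assigned to each health state and the running of the Markov model will provide the time spent" in each state. Future costs and effects are discounted at 3%. Under Analysis, univariate and probabilistic sensitivity analyses will vary the main transition, utility and cost inputs. No relative risk, hazard ratio or state-specific death rate for diabetes or prediabetes is stated in 9.4.9.

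**The concern.** The trial effect enters the lifetime model through projected diabetes incidence. Avoiding or delaying diabetes can then change QALYs in two ways: people spend more time in a state with a higher utility, and they live longer. If every living state has the same age-specific death probability, the second way is closed. This sits poorly with the reason given for choosing QALYs, which includes mortality. It also sits poorly with the protocol's own background: section 2.2 says "Prediabetes has been linked to an approximately 20% increased risk of cardiovascular disease" and reports 14% higher cancer mortality in prediabetes.

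Cost-effectiveness is in the trial's title and is a listed objective. Because few conversions are expected within 12 months, the lifetime result depends on what the model attaches to diabetes avoided later. Incremental QALYs are the denominator of the cost-effectiveness ratio that will be compared with a willingness-to-pay threshold.

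**Working it through.** The plan states no life-year, mortality-ratio or cost-effectiveness figure here, so there is none to reproduce. The check has a structural step and an illustrative one.

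**1. Structure.** Let P(t) and D(t) be the proportions alive without and with diabetes in year t, p the annual diabetes incidence, m(t) the life-table death probability, and r the mortality ratio for diabetes, with mD(t) = 1 − (1 − m(t))^r.

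- P(t+1) = P(t)·(1 − m(t))·(1 − p)
- D(t+1) = D(t)·(1 − mD(t)) + P(t)·(1 − m(t))·p

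With r = 1, mD = m, and adding the two lines gives P(t+1) + D(t+1) = (P(t) + D(t))·(1 − m(t)). The incidence p drops out. Survival is the same in both arms whatever their diabetes incidence, so the life-year difference is exactly 0.

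**2. Illustrative size.** From the documents: 3% discounting. Table 1 gives mean ages of 54 and 57, and I start at 55. Assumed, not in the documents: m(t) = 0.006·exp(0.085t), annual cycles to age 110; utilities 0.90 without and 0.80 with diabetes; annual incidence 5% vs 3%, 8% vs 5% or 10% vs 5%; r = 1.0, 1.15, 1.5 or 2.0; no excess mortality in prediabetes.

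Discounted life-years = Σ(P + D)/1.03^t. Discounted QALYs = Σ(0.90P + 0.80D)/1.03^t. The entries are lower-incidence minus higher-incidence strategy, as discounted life-years / discounted QALYs:

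| r | 5% vs 3% | 8% vs 5% | 10% vs 5% |
|---|---|---|---|
| 1.0 (as written) | 0 / 0.2273 | 0 / 0.2340 | 0 / 0.3444 |
| 1.15 | 0.0892 / 0.2986 | 0.0837 / 0.3010 | 0.1197 / 0.4401 |
| 1.5 | 0.2606 / 0.4358 | 0.2465 / 0.4312 | 0.3532 / 0.6270 |
| 2.0 | 0.4473 / 0.5851 | 0.4264 / 0.5752 | 0.6126 / 0.8345 |

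Share of the QALY difference that the plan as written recovers (first row divided by the row in question):

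- r = 1.15: 0.2273/0.2986 = 76%, 0.2340/0.3010 = 78%, 0.3444/0.4401 = 78%
- r = 1.5: 0.2273/0.4358 = 52%, 0.2340/0.4312 = 54%, 0.3444/0.6270 = 55%
- r = 2.0: 0.2273/0.5851 = 39%, 0.2340/0.5752 = 41%, 0.3444/0.8345 = 41%

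If the cost difference were held fixed, the absolute cost per QALY would be inflated by the inverse: about 1.3 times at 1.15, 1.8-1.9 times at 1.5 and 2.4-2.6 times at 2.0. The cost difference would not stay fixed, because people who live longer also accrue costs, so these factors show sensitivity and do not predict the ratio.

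**3. Loss per case.** With hazard 0.007·r·exp(bt) from age 55 and b = ln2/8.5 (again assumed), diabetes held from 55 for life costs 1.4, 3.9 and 6.6 years at r = 1.15, 1.5 and 2.0, or 0.6, 1.9 and 3.2 discounted. With onset ten years later, averaged over the same starting cohort, the discounted losses are 0.4, 1.3 and 2.2.

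**The case against.** The strongest reply is that saying life tables are used to determine death probabilities does not say the rates are equal or unadjusted. They could be a base rate to be multiplied by state-specific ratios. Death is listed among the states, transitions may draw on published literature as needed, and the states themselves are only examples, so this part of the plan is an outline. That reading is possible, but no multiplier is written. The specific sentence on death follows the general one on transitions, names its own source and covers all states.

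A second reply is that moving into death is a transition, so the planned sensitivity analyses would cover it. They would if a diabetes mortality ratio existed to be varied. Varying one life table shared by all states leaves the life-year difference at zero.

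Third, the size depends on assumptions, and this stands. The incidence gaps of 2 to 5 percentage points are generous for two active programmes that section 9.1 assumes equally successful; if projected incidence is equal, nothing is lost. Any excess mortality in prediabetes would narrow the contrast, and section 2.2 reports similar rates of myocardial infarction and stroke in prediabetes and diabetes.

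A reader might also infer a flat contradiction between the mortality sentence and either the QALY rationale or the background section. The documents do not go that far: the rationale concerns the choice of measure, the model does have a death state, and section 2.2 is not a model input.

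**Conclusion.** The point holds as a matter of structure. Followed literally, the stated rule makes survival independent of diabetes status and removes life-years from the between-arm comparison. This rests on the tables being general-population rates not split by glycaemic status, which the documents do not state. Under the assumed inputs, the plan as written recovers roughly three quarters of the discounted QALY difference at a diabetes mortality ratio of 1.15, a little over half at 1.5 and about two fifths at 2.0.

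Two stronger conclusions are not supported. One is that preventing diabetes is worth nothing in this model: 0.23 to 0.34 discounted QALYs remain in the illustration through utilities, and state costs still differ. The other is that several life-years are lost to the comparison: that is a loss per lifetime case from age 55, whereas the illustrated between-strategy difference is 0.08 to 0.61 discounted life-years. The attenuation runs in whichever direction the QALY difference points, so it does not favour one arm by design, and it could understate harm from the less effective programme. The matter should be corrected, but it is confined to the secondary lifetime analysis.

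**What to change.** Replace the mortality sentence in 9.4.9 with text to this effect:

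- Age- and sex-specific life-table rates are the population background. The rate for normal glucose tolerance is obtained by rescaling: m0(a) = m_pop(a) / Σ w_k(a)·r_k, where w_k is the prevalence of glycaemic state k at age a and r_k its mortality ratio. The prevalence-weighted average over states then reproduces the life table. Assigning the unscaled table to normal glucose tolerance and multiplying upward would count twice the excess deaths already in population rates.
- Published mortality ratios are applied to the type 2 diabetes state, and to the prediabetes states if the literature supports them. Name the source, value and reference group of each ratio.
- The ratios are varied in the univariate and probabilistic sensitivity analyses, with 1.0 for all states kept as a scenario.

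The cost is one or two more literature-based parameters with their uncertainty, plus prevalence weights for the rescaling. The plan already takes transitions, utilities and state costs from published work. No new data are collected, and the sample size and primary analysis do not change.

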##### **Costs**

Costs will be estimated using a health system perspective and consist of formal healthcare costs and informal healthcare costs in accordance with best practices. Healthcare costs will be estimated using healthcare resources utilized multiplied by prices for resources. We anticipate that healthcare utilization costs during the trial will be similar between arms. Future healthcare utilization costs will be projected based on previously published literature in relation to our metabolic endpoints. We will use patient reported medical history and medication (Section 11.4) and healthcare utilization (Section 11.14) collected baseline, 6 months, and 12 months during the study to quantify healthcare resources utilized. Unit prices will be derived from public database and Medicare fee schedules. We will use published data to supplement cost data including cost estimates for each health state in the Markov model. Intervention costs will be estimated from data provided to us by the company developing the app, Sweetch Health, Ltd. Costs for the human coach intervention in the hDPP arm will be estimated using the Medicare Diabetes Prevention Program (MDPP) billing and fee schedule.

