#### 9.4.5 COVARIATE ADJUSTMENT

We anticipate that randomization will minimize differences in participant characteristics that may be associated with the primary or secondary endpoints between the two groups. All primary statistical analyses will be unadjusted. However, if we identify differences in participant baseline characteristics, or exposure to potential confounders during the course of the study (e.g. steroid use, antihyperglycemic use), sensitivity analyses will be conducted to include these variables as covariates in multivariable logistic or linear regression models, as appropriate. These adjusted analyses will be viewed as supportive in interpreting the findings of the unadjusted analyses.

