**11.14 HEALTHCARE UTILIZATION**

How many times did you visit your primary care provider in the past 6 months?	
How many times did you visit a non-primary care specialist in the past 6 months?	
Why did you see a non-primary care specialist?	
How many times were you hospitalized in the last 6 months?	
Why were you hospitalized?	
How many times did you go to the emergency department in the past 6 months?	
Why did you visit the emergency department?	
What is the name of your primary care provider?	
What is your primary care provider's address?	

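### Baseline healthcare use is collected but has no covariate role in the 12-month cost difference; adjusting for it would gain precision at no cost

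*Combined protocol and SAP*

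**What the plan says.** Cost-effectiveness is a listed secondary endpoint (Section 3.3). Section 9.4.9 sets the shorter-term analysis as follows: "For the 12-month horizon, we will evaluate the differences in costs and effects for participants in the dDPP and hDPP study arms". On how costs are built, the Costs paragraph says: "Healthcare costs will be estimated using healthcare resources utilized multiplied by prices for resources". The resource data are participant-reported medical history and medications (Section 11.4) together with "healthcare utilization (Section 11.14) collected baseline, 6 months, and 12 months during the study to quantify healthcare resources utilized".

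The utilisation form in Section 11.14 looks back half a year, for example "How many times did you visit your primary care provider in the past 6 months" and "How many times were you hospitalized in the last 6 months". The Schedule of Activities places it at baseline, day 180 and day 365.

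Section 9.4.9 names no regression model or covariate for cost, and its sensitivity analyses vary only transition, utility and cost parameters. The general rule in Section 9.4.5 is "All primary statistical analyses will be unadjusted". If baseline differences or confounding exposures are identified, "sensitivity analyses will be conducted to include these variables as covariates in multivariable logistic or linear regression models, as appropriate", and those results are treated as supportive. Cost and utilisation are not mentioned there. Section 9.4.3 does not name utilisation among the baseline characteristics to be reported, and Section 6.4 stratifies only on baseline A1C level and site.

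**The concern.** A person's past use of care usually predicts their later use. Here the baseline value of the utilisation outcome will be in the database for every participant, but the plan does not say what it is for. It is listed alongside the two follow-up collections as a source for resources used, and no covariate role is stated.

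Prior use is balanced between arms only by chance, because it is not a stratification factor. Section 9.4.9 expects utilisation costs in the trial year to be similar between arms. If so, utilisation contributes mainly noise to the incremental cost, and any chance difference in prior use feeds through to it. What is at stake is the width of the interval around the 12-month incremental cost, and how far that estimate can be moved by differences that existed before either programme began. The primary endpoint is not affected.

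**Working it through.** **Inputs from the documents.** Half-year recall at baseline, 6 and 12 months (Section 11.14 and the Schedule of Activities); 138 analysable and 184 randomised per arm (Section 9.2). The plan gives no sample size, standard deviation or precision for cost.

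**The plan's own figure.** With 50% success in both arms, a margin of 0.15, one-sided 5% and 80% power: n = 2 × 0.25 × (1.645 + 0.842)² / 0.15² = 137.4, so 138 per arm; 138 / 0.75 = 184. Both reproduce. They concern the primary endpoint, and 138 is borrowed below only to put standard errors on a scale.

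**Assumption.** Let B be use in the half-year before baseline, and F1 and F2 the two half-years on trial. Each has variance 1 (units: the SD of one half-year's cost), and every pair has correlation r. The documents give no value, so r runs from 0.1 to 0.7.

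**Formulas.**
- 12-month cost without adjustment: Var(F1 + F2) = 2 + 2r.
- Covariance with baseline: Cov(B, F1 + F2) = 2r.
- Variance after adjustment for B: 2 + 2r − 4r².
- SE of the between-arm difference: √(2/n × variance), with √(2/138) = 0.120.
- SE ratio, unadjusted to adjusted: √[(2 + 2r) / (2 + 2r − 4r²)], which does not depend on n.

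| r | Variance unadjusted | Variance adjusted | SE unadjusted | SE adjusted | SE ratio |
|---|---|---|---|---|---|
| 0.1 | 2.20 | 2.16 | 0.179 | 0.177 | 1.01 |
| 0.3 | 2.60 | 2.24 | 0.194 | 0.180 | 1.08 |
| 0.5 | 3.00 | 2.00 | 0.208 | 0.170 | 1.22 |
| 0.7 | 3.40 | 1.44 | 0.222 | 0.145 | 1.54 |

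Simulating 8,000 trials at each of r = 0.3, 0.5 and 0.7 gave unadjusted SEs of 0.194, 0.208 and 0.223, and adjusted SEs of about 0.18, 0.17 and 0.14. Both estimators averaged within 0.005 of zero when there was no true difference.

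**Chance imbalance.** At 138 per arm, 95% of randomisations leave a baseline difference within ±1.96 × 0.120 = ±0.24 SD. Without adjustment, each 0.1 SD of imbalance is expected to move the 12-month cost difference by 0.1 × 2r: 0.02 SD at r = 0.1, 0.06 at 0.3, 0.10 at 0.5 and 0.14 at 0.7. With adjustment the expected movement is about zero.

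**The case against.** The strongest reply is that nothing here is invalid. An unadjusted comparison of randomised arms is unbiased, and its standard error already allows for chance imbalance. That stands: this is a more efficient estimator, not the correction of an error, and the gain is negligible if use is weakly correlated over time.

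It can also be said that the plan has relevant provisions. Section 9.4.1 assigns linear regression to continuous secondary measures, and Section 9.4.5 allows adjusted sensitivity analyses. A reader might infer that the plan rules out adjustment of cost altogether, and the documents do not support that. But the cover is partial: the adjustment is conditional on differences being found, is supportive only, and names neither cost nor utilisation.

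A reader might also infer from the Costs sentence that baseline use is added in, so that 18 months of use enter a 12-month cost. That reading is strained. Section 9.4.9 fixes a 12-month horizon and speaks of utilisation within the trial year, and the sentence can be read simply as a collection schedule for two instruments. Nothing says the three collections are summed. It is an ambiguity worth removing in the same edit, and no size is claimed for it.

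Finally, how much utilisation noise reaches the acceptability curve is unknown. Programme costs come from company data and the Medicare fee schedule, and published data supplement the health-state costs. That also stands, so the claim stops at the 12-month cost difference and the ICER built on it.

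**Conclusion.** This is a free improvement to a secondary analysis. The plan collects the baseline value of its utilisation outcome and does not say it will be used as a covariate in the 12-month cost comparison. The price is an unadjusted standard error about 1% to 54% larger than the adjusted one across r = 0.1 to 0.7, with 8% at 0.3 and 22% at 0.5, plus exposure to chance imbalance in prior use.

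The figures rest on equal variances and a common pairwise correlation between half-year windows, and the documents support no particular value of r. They describe the utilisation component of cost; medications and programme payments are outside the calculation. Restating the gain as statistical power would go beyond the plan, which sets no test or detectable difference for cost and judges the ICER against a willingness-to-pay threshold. Nor is there systematic bias: under randomisation, the comparison without adjustment is centred on the right value.

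**What to change.** In Section 9.4.9:

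- State that 12-month resource use is counted from the 6- and 12-month collections, covering both the Section 11.14 utilisation form and the Section 11.4 medication data, and that the baseline collection serves only as a covariate and is not added to the total. Naming both instruments matters because Section 11.14 has no medication item.
- Estimate the incremental 12-month cost by regression on arm, with each participant's baseline 6-month utilisation cost and the randomisation strata (baseline A1C level and site) as prespecified covariates.
- Carry the adjusted difference and its uncertainty into the 12-month ICER.
- Say that this is the specified analysis for cost, so that it is not read as falling under the conditional, supportive adjustment in Section 9.4.5.

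The cost is a few sentences of text. All the data are already scheduled, with no added participants, visits or procedures. Settling it before the cost data are analysed also avoids a later choice between adjusted and unadjusted results.
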